# Reportable Events

The data with respect to adverse event (AE) severity and attribution of any adverse outcomes to study interventions or procedures will be based on coding procedures endorsed by the YALE IRB, as follows:

Coding of Severity:

- 0 = No adverse event or within normal limits
- 1 = Mild adverse event
- 2 = Moderate adverse event
- 3 = Severe, resulting in psychiatric or medical hospitalization
- 4 = Life-threatening adverse event
- 5 = Fatal adverse event

Coding of Attribution:

- 1 = Unrelated to study interventions
- 2 = Unlikely relationship to study interventions
- 3 = Possible relationship to study interventions
- 4 = Probable relationship to study interventions
- 5 = Definite relationship to study interventions

Event attribution may include the following study components: 1) Interventions; 2) Research Assessments; or 3) Study Procedures. On the basis of this review, after [name] excuses herself, the DSMB's outside reviewers will deliberate, and submit a written report to the P.I., the Yale IRB and the Program Officer within 48 hours of these meetings, suggesting any recommendations for protocol modifications, or a recommendation to terminate the trial. While no unblinded interim data analysis is planned, if the DSMB independent reviewers suggest that an unblinded interim analysis is required, we will consult with the program official and the IRB, and a statistical penalty for this interim analysis may be taken if it is decided that the trial can continue. All adverse events graded 3 or higher in severity and attribution will be considered as serious adverse events (SAEs), and will be reported within 48 hours to the Yale IRB HIC, and NIH. Reasons for terminating a subject's participation (e.g. "stopping rules") will include: 1) serious adverse reaction to study intervention Fathers for Change or BIP. Anticipated adverse events include increased negative mood, increased danger to female partner or child, and/or rearrests related to IPV or CM offenses or other non-family violence criminal charges. These will be assessed with rating scales. As these scales are assessed at baseline and during the experimental procedure, we will be able to determine if the event is attributable to the research. Otherwise, routine reporting of adverse events data will be done on a quarterly basis corresponding to the quarterly meetings of this study's DSMB, using the following summary table which includes AE severity and attribution, as well as whether or not such AEs were anticipated (ATP) or unanticipated (UNATP).

4. **Potential Benefits:** Identify any benefits that may be reasonably expected to result from the research, either to the participant(s) or to society at large. (*Payment of participants is not considered a benefit in this context of the risk benefit assessment.*)

The major potential benefit of this study is the development of a feasible, evidence-based intervention that may be integrated into treatment clinics that addresses the intersecting issue of IPV and CM especially for those that have already failed the standard treatment as usual group Batterer Intervention program. The proposed intervention may decrease IPV and CM, which will benefit the men their co-parents and children. Additionally, male participants will be offered free treatment.

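### The SAE definition requires attribution as well as severity, so hospitalisations, life-threatening events and deaths judged unrelated or unlikely move from 48-hour to quarterly reporting

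*Combined protocol and SAP*

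**What the plan says.** All references are to the combined protocol and SAP, mainly Section VII, item 3 (Data and Safety Monitoring Plan).

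Reportable Events sets up two separate scales. On the severity scale, which runs from 0 to 5, the top three grades are "3 = Severe, resulting in psychiatric or medical hospitalization", "4 = Life-threatening adverse event" and "5 = Fatal adverse event". On the attribution scale, which runs from 1 to 5, the lowest three grades are "1 = Unrelated to study interventions", "2 = Unlikely relationship to study interventions" and "3 = Possible relationship to study interventions".

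The same subsection then joins the scales into one definition: "All adverse events graded 3 or higher in severity and attribution will be considered as serious adverse events (SAEs". Such events "will be reported within 48 hours to the Yale IRB HIC, and NIH". A later sentence, opening with the word otherwise, sends the remaining adverse event data to a quarterly summary timed to the DSMB meetings. That summary shows severity, attribution and whether the event was anticipated.

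Roles and Responsibilities says the DSMB meets quarterly and reviews aggregated data presented blinded. The DSMB is not named as a recipient of the 48-hour report.

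**The concern.** Seriousness describes the outcome of an event; relatedness is a judgement about its cause. The plan scores them separately and then makes the first depend on the second. How quickly a death reaches the IRB and NIH therefore turns on a causality code assigned before those bodies have seen the event.

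This matters here because the plan rates the trial as greater than minimal risk and lists greater danger to a partner or child among the anticipated adverse events. Violence is also the behaviour being treated, so a serious incident can be put down to the father's history rather than to the intervention.

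The rule also sits awkwardly beside Trial Safety. There, suicidal ideation that leads to hospitalisation ends participation in the intervention, with no condition on cause. Under Reportable Events the same event has severity 3, yet it is not an SAE if its attribution is coded 1 or 2.

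**Working it through.** The plan gives no figure to reproduce. The check applies the stated cut-offs to every combination of the two scales and then looks for another expedited route.

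**Step 1. Apply the rule as written (severity at least 3 and attribution at least 3).**

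| Severity | Attribution 1 (unrelated) | Attribution 2 (unlikely) | Attribution 3 to 5 (possible to definite) |
|---|---|---|---|
| 3, hospitalisation | quarterly | quarterly | SAE, 48 hours |
| 4, life-threatening | quarterly | quarterly | SAE, 48 hours |
| 5, fatal | quarterly | quarterly | SAE, 48 hours |

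The scales give 6 × 5 = 30 combinations. Severity 3 to 5 accounts for 3 × 5 = 15, and the rule makes 3 × 3 = 9 of them SAEs. The remaining 15 − 9 = 6 are (3,1), (3,2), (4,1), (4,2), (5,1) and (5,2). Four of these, 2 × 2, are life-threatening or fatal.

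**Step 2. Test the other reading.** If the rule meant a score of 3 on either scale, the only non-SAEs would be severity 0 to 2 with attribution 1 or 2, which is 3 × 2 = 6 combinations. That leaves 30 − 6 = 24 SAEs. Of these, 24 − 15 = 9 would have severity 0 to 2, including grade 0, which denotes no adverse event. That cannot be intended, so the reading requiring both scores stands. The quarterly default for everything else fits it.

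**Step 3. Look for another expedited route to the IRB or NIH.**

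- Roles and Responsibilities requires an immediate telephone call about significant safety concerns, but within the study team.
- Minimizing Risks (Section VII, item 2) provides at least weekly clinical monitoring, with immediate contact to senior clinicians. It also provides for notice to the partner and police after a credible threat.
- Section V, item 8 covers child-abuse reports and suicidal or homicidal intent. These lead to protective services, a higher level of care or the threatened partner.
- The item on adverse event reporting in multi-site studies (Section VII, item 3d) still holds only the template prompt.
- Reportable Events has a second 48-hour clock, for the DSMB's written report to the investigator, the IRB and the program officer. It runs from the DSMB meeting, not from the event.

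None of these takes a severity 3 to 5 event with attribution 1 or 2 to the IRB or NIH promptly.

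**Step 4. Size the delay.** A quarter is 12 / 4 = 3 months. An event just after one quarterly report may wait about three months for the next, against 48 hours = 2 days for an SAE. Three months is a maximum; an event just before a meeting waits much less.

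**The case against.** The strongest reply has four parts.

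- The attribution cut-off is set at possible, the lowest grade that accepts any link. An event whose cause is truly arguable should be coded 3 and reported within 48 hours. Only events actively judged unrelated or unlikely drop out. This stands, and it narrows the gap. It does not close it, because an early code of unlikely may be wrong and the rule delays outside sight of it.
- Several safeguards have no attribution condition: the internal call, weekly monitoring, and reports to protective services, partner or police. They limit the harm from delay but do not give the IRB or NIH the event.
- The coding procedures are described as endorsed by the IRB. That sentence introduces the two scales; it does not expressly cover the rule that combines them, and endorsement would not change the rule's effect.
- IRB or NIH policy may separately require prompt reporting of deaths. The documents do not show this either way.

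A reader might also infer more than the text supports:

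- That the six combinations in the table measure the share of serious events missed. They are cells in a grid; the documents give no event rates and no distribution of attribution codes.
- That serious events go uncounted. They lose the SAE label and are reported later, but the quarterly table still carries them with both grades.
- That the rule hides a pattern in one arm. Single 48-hour reports would not reveal an imbalance between arms either, and the DSMB sees aggregated, blinded data.
- That the study team alone decides attribution. The plan does not say who assigns the code.

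**Conclusion.** The concern holds as a defect in the reporting rule. Events of severity 3, 4 or 5 coded unrelated or unlikely are not SAEs under this plan, and they reach the IRB and NIH through the quarterly route, up to about three months later instead of within 48 hours. How many events this would affect cannot be estimated from the documents.

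The conclusion rests on three assumptions: that both scores must reach 3, that quarterly reporting runs to schedule, and that no institutional requirement outside these documents overrides the rule. The consequence is for the timeliness of safety oversight. No estimate, test or sample size is affected.

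The DSMB's late sight of events is a separate gap. It applies even to qualifying SAEs, because the 48-hour route names only the IRB and NIH, so the attribution condition does not cause it.

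**What to change.** First change, in Reportable Events: define an SAE as any adverse event of severity grade 3 or higher, whatever its attribution. Keep attribution as a separately recorded field, and report every such event to the IRB and NIH within 48 hours with the attribution code shown. The quarterly table already displays both grades and needs no change.

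Second change, to be decided on its own merits: add the DSMB to the 48-hour recipients. Correcting the definition alone would not do this.

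Both are changes of wording. The cost is some additional expedited reports, in a number the documents do not allow to be estimated, and for the second change some further work for the DSMB between meetings.

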# Phase II:

The target sample is 280 father-coparent dyads and their 9 months to 11 year-old children recruited from CPS-involved families referred to the Parent and Family Development Program (PFDP) at Yale or the UCONN Health Center Outpatient Psychiatry Clinic. Participants will be randomized to either F4C (n = 140) or BIP (n = 140) following a baseline assessment. Half of F4C and BIP families will be treated at Yale and half at UConn Health. Yale will serve families in

Greater New Haven region, while UConn Health will serve families in the Greater Hartford region. The two sites are approximately a 45-minute drive apart.

5. **Describe** how access to the population will be gained in the study.

Fathers referred to the Parent and Family Development Program or UCONN Health Center by the CT Department of Children and Families (DCF) or the community due to IPV or child maltreatment risk will be provided information about the study and asked to complete an initial brief screening if they are interested in participation. He will be told that his screening questionnaire (which will include demographic matching information such as age, ethnicity, city of residence, income, employment history, SA history etc.) will be reviewed and he will be contacted to set up further assessment sessions if he is found eligible by the PI based on our study's requirements. This will provide the opportunity for contact with the mother to conduct phone screening with her related to IPV and her willingness for their shared child to participate. Female co-parent and intimate partner contact information will be provided on the referral from DCF or community referral source so that fathers are not providing this information, and this will limit the possibility of coercion.

6. **Participant classification:** Check off all classifications of participants that will be specifically recruited for enrollment in the research project. Will participants who may require additional safeguards or other considerations be enrolled in the study? If so, identify the population of participants requiring special safeguards and provide a justification for their involvement.

🛛 Healthy	□Fetal material, placenta, or dead fetus
Prisoners	□Economically disadvantaged persons
🗆 Employees	□Pregnant women and/or fetuses
□ Females of childbearing pote	ential
	
 
Healthy
 
Prisoners
 
Employees
 
Females of childbearing pote
 

Click or tap here to enter text.

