# Summary of the Protocol

As detailed in the research plan and the protection of human subjects sections this study involves a randomized controlled trial of Fathers for Change compared to Batterer Intervention Program. For further details on the sample and inclusion/exclusion criteria, see the Human Subjects section. The Yale School of Medicine Child Study Center Parent and Family Development Program clinic will serve as the participating site. The clinics will recruit participants, allow for data collection/assessments by study staff and offer space for provision of the study treatments.

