# **Roles and Responsibilities**

[name] and the study team will review data integrity and safety during weekly team meetings. The post graduate associate and research interns will review assessment data and bring any concerns to [name] immediately if needed or in the context of weekly study review. Drs. [name] (Fathers for change) and [name] (Batterer Intervention) will also provide weekly supervision to study therapists, where they can report any concerns or safety considerations related to study interventions. Any significant study safety concerns related to participants will result in an immediate phone call to [name] and if needed Drs. [name] and [name]. [name] will not participate in data analysis. [name] or another team member masked to participant treatment group will carry out all statistical analyses related to study intervention comparisons.

In accordance with Federal and Institutional regulations, a Data Safety and Monitoring Board (DSMB) for this study will meet quarterly to review aggregated study outcomes data and adverse events. The DSMB will be composed of three clinical investigators with expertise in working with men/fathers, forensic populations, and IPV victims/child witnesses who are not affiliated with this study. [name] will present these aggregated data on study outcomes and adverse events quarterly in a blinded fashion.

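### The DSMB is not a 48-hour recipient of serious adverse events, and a fatal or life-threatening event rated unrelated or unlikely has no 48-hour route at all

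*Combined protocol and SAP*

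**What the plan says.** All of the reporting text is in Section VII, item 3 (Data and Safety Monitoring Plan).

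- **Definition.** Reportable Events states: "All adverse events graded 3 or higher in severity and attribution will be considered as serious adverse events (SAEs". Severity runs from 0 to 5, and the top two codes are "4 = Life-threatening adverse event" and "5 = Fatal adverse event". Attribution runs from 1 (unrelated) and 2 (unlikely) up to 5 (definite).
- **Expedited route.** These events "will be reported within 48 hours to the Yale IRB HIC, and NIH". No other recipient is listed.
- **The board.** Roles and Responsibilities says that "a Data Safety and Monitoring Board (DSMB) for this study will meet quarterly to review aggregated study outcomes data and adverse events". Reportable Events ties all other adverse event reporting to those quarterly meetings. It has the board's outside reviewers send a written report to the PI, the Yale IRB and the Program Officer within 48 hours of each meeting. That report may recommend protocol changes or termination.
- **Anticipated events.** The same section lists "increased danger to female partner or child" among the anticipated adverse events.
- **Sites.** Summary of the Protocol says that the Yale "Parent and Family Development Program clinic will serve as the participating site". Section IV, item 4 (Phase II) says: "Half of F4C and BIP families will be treated at Yale and half at UConn Health". Section V, item 3 gives a Yale target of 180 fathers out of 280 across all sites. The three multi-site items in Section VII, item 3(d) contain only the template prompt.

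**The concern.** The investigators rate the overall risk as greater than minimal, and the harms they anticipate include harm to people other than the treated father. The DSMB is the only body in the plan described as independent of the study and able to recommend modification or termination. Under the written route, two bodies hear of a serious adverse event within two days, while the board waits for its calendar.

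The definition adds a second gap. Violence toward a partner or child is what brings fathers into this trial, so whether a given assault is related to the intervention is a hard judgement. The plan makes expedited reporting depend on it even for the two highest severity grades. A fatal event judged unlikely to be related would first surface in quarterly reporting.

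**Working it through.** The plan gives no figure to reproduce. The check compares the reporting routes and counts the grade combinations that reach each one.

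**1. When each body is told**

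| Body | Written input | Longest written interval |
|---|---|---|
| Yale IRB HIC | 48-hour report | 2 days |
| NIH | 48-hour report | 2 days |
| DSMB | Quarterly meeting and quarterly table | One quarter, about 3 months (roughly 90 days) |

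The DSMB figure assumes evenly spaced meetings and an event just after one of them. The other 48-hour period in Reportable Events does not shorten it: that is the board's outgoing report after a meeting, not notice to the board. Roles and Responsibilities requires an immediate telephone call about significant safety concerns, but does not mention onward notice to the DSMB or an unscheduled meeting.

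**2. What counts as serious**

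Read as written, the rule needs severity of 3 or more and attribution of 3 or more.

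- Severity 3 to 5 by attribution 1 to 5: 3 × 5 = 15 combinations.
- Meeting the rule (attribution 3 to 5): 3 × 3 = 9.
- Not meeting it (attribution 1 or 2): 3 × 2 = 6.
- Of those 6, life-threatening or fatal (severity 4 or 5): 2 × 2 = 4.

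So 9 of 15 combinations reach the IRB and NIH within 48 hours, none reaches the DSMB on that clock, and 6 reach nobody on it. These are counts of grade combinations, not expected numbers of events; the documents give no event rates.

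**3. Effect of the change proposed below**

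The DSMB would receive within 48 hours the 9 combinations already defined as serious plus the 4 life-threatening or fatal ones with low attribution: 9 + 4 = 13 of 15. The other 2 (severity 3, attribution 1 or 2) stay on the quarterly route.

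**4. Site statements**

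- By Section IV, item 4: UConn Health treats half of 280, which is 140 (50%).
- By Section V, item 3: 280 − 180 = 100, and 100/280 = 35.7%.
- By Summary of the Protocol: the Yale clinic is the participating site.

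The three statements do not agree. On either count a second treating site exists, and the items meant to describe multi-site adverse event handling are unfilled template fields rather than redactions.

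**The case against.** Several points on the other side stand.

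- **The delay is a worst case.** Nothing prevents the study team from telling the DSMB sooner or the board from meeting early. The plan simply does not require or provide for either.
- **Individual participants have other protection.** Section VII, item 2 requires immediate contact with senior clinicians on serious deterioration. Roles and Responsibilities requires an immediate call and weekly team review, and Trial Safety sets out grounds for ending a father's participation. The gap is in independent oversight, not in acute response.
- **The IRB and NIH do hear early and can act.** This is so for events that meet the definition. The plan does not ask them to alert the board.

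A reader might also draw three stronger conclusions, which the documents do not support.

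- **That the safety review leaves out UConn.** The operative sentences set up a board for the study and cover all adverse events, without limiting either to Yale. The sentence after the one naming the Yale clinic speaks of clinics in the plural, which suggests outdated wording rather than exclusion.
- **That nothing carries a UConn event to the lead site.** Section V, item 8 sends staff to the PI at their own site, and the immediate calls in Section VII are not limited by site. The recipients' names have been removed and may include the lead investigator. The summary table mentioned in Reportable Events is not in the text available, so a site field in it cannot be ruled out.
- **That the DSMB is the body assigned to stop the trial if violence increases.** Trial Safety states that rule without naming who applies it, and the board's stated role is to recommend.

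**Conclusion.** The point holds for the reporting rule. The DSMB is absent from an explicit list of expedited recipients and, under the plan as written, may learn of a serious adverse event up to about 3 months later. Separately, 4 combinations of fatal or life-threatening severity with low attribution have no 48-hour route to any body. Adding the DSMB to the existing list would not cure this second gap, because the definition screens those events out first.

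This rests on reading the recipient list as complete, on the joint reading of severity and attribution, and on evenly spaced quarterly meetings.

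The site matter is secondary. It is an inconsistency between sections plus an unfilled part of the monitoring plan. It does not show that UConn families are outside safety review. Nothing here affects the efficacy analysis. The change is worth making because the gap concerns the most serious events and costs little to close.

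**What to change.** In Reportable Events:

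1. Add the DSMB to the recipients of the 48-hour report.
2. State that the DSMB may convene outside the quarterly cycle on receipt of such a report.
3. State that every event of severity 4 or 5 goes to the DSMB on the same 48-hour clock, whatever its attribution grade.

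To reconcile the site text:

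4. Bring Summary of the Protocol into line with Section IV, item 4 on which sites take part, and settle the Phase II site numbers between Section IV, item 4 and Section V, item 3.
5. Complete Section VII, item 3(d), stating that UConn Health events enter the same 48-hour report and the same quarterly table.

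The cost is a wording amendment, one more recipient on a report already being written, a few more expedited reports, and occasional unscheduled DSMB calls. Eligibility, treatment and the analysis are unchanged.
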